## 1. Glossary

Term	Abbreviation	Definition
Adverse Event	AE	
Any untoward medical occurrence, unintended disease or injury, or untoward clinical signs (including abnormal laboratory findings) in patients, users or other persons, whether or not related to the investigational medical device.
 
NOTE 1 This definition includes events related to the investigational medical device or the comparator.
 
NOTE 2 This definition includes events related to the procedures involved.
 
NOTE 3 For users or other persons, this definition is restricted to events related to investigational medical devices.

Adverse Device Effect	ADE	
Adverse event related to the use of an investigational medical device.
 
NOTE 1 This definition includes adverse events resulting from insufficient or inadequate instructions for use, deployment, implantation, installation, or operation, or any malfunction of the investigational medical device.
 
NOTE 2 This definition includes any event resulting from use error or from intentional misuse of the investigational medical device.

Admit, Discharge, Transfer	ADT	Software application used by healthcare facilities to track patients from the point of arrival at a hospital until departure by transfer, discharge, or death.
American Society of Anesthesiologists physical status classification system	ASA PS	A surgical risk classification scale based upon health status assessment with range of ASA I - ASA VI.
Assess Respiratory Risk in Surgical Patients in Catalonia Score	ARISCAT Score	ARISCAT Score is an accurate risk score for predicting high or intermediate risk for postoperative pulmonary complications in patients undergoing surgery, calculated based on preoperative data such as on patient's age, preoperative SpO 2 , respiratory infection, anemia, surgery type and duration.
Capnography	CO 2 monitoring	A non-invasive method for monitoring the level of carbon dioxide in exhaled breath (etCO 2 ).

Term	Abbreviation	Definition
Clinical Investigation Plan	CIP	The present document describing LIFEGUARD Study Protocol.
Code Blue	Code Blue	An emergency situation in which a patient is in cardiopulmonary arrest, requiring a Rapid Response Team (see definition) to rush to the specific location and begin immediate resuscitative efforts.
Electronic Medical Records	EMR	A digital version of medical record that contains all of a patient's medical history in one practice.
Early Warning Score	EWS	Physiologic track and trigger systems, based on patients' vital signs, used to monitor adult patients in acute hospital settings to prevent Adverse Events.
Electronic Case Report Forms	eCRF	Forms where the clinical data are collected. eCRF is the electronic version of case report forms.
Ethical Committee	EC	Any board, committee, or other group formally designated by an institution to review, to approve the initiation of, and to conduct periodic review of, biomedical research involving human patients. The primary purpose of such review is to assure the protection of the rights and welfare of the human patients.
End Tidal CO 2	etCO 2	The numeric partial pressure of the maximum value of carbon dioxide in the exhaled breath over the last 20 seconds. The etCO 2 numeric value is updated once a second.
Intensive Care Unit	ICU	Acute care with 24 hour coverage. Patients may be directly transferred from the OR to the ICU or via the PACU.
Integrated Pulmonary Index™	IPI	The Integrated Pulmonary Index (IPI) is a composite index of etCO 2 , SpO 2 , RR and PR that is intended to indicate changes in physiological status as indicated by the monitored variables and cleared by FDA (K082268) in 2009.
Preoperative Score to Predict Postoperative Mortality Score	POSPOM Score	POSPOM Score is an accurate risk score for predicting in-hospital mortality in patients undergoing surgery, calculated based on preoperative data such as on patient's age, planned

Term	Abbreviation	Definition
		surgery and presence of additional diseases or disorders.
Pulse Rate	PR	Pulsatile cycle in beats per minute via pulse oximeter technology.
Pulse Oximetry	SpO 2	Depends on pulsatile blood flow and measures only the oxyhemoglobin in arterial blood as it leaves the heart.
Rapid Response Team	RRT	A team of health care providers that responds to hospitalized patients with early signs of deterioration on non-intensive care units to prevent respiratory or cardiac arrest.
Respiratory Compromise	RC	Respiratory compromise consists of respiratory insufficiency, compromise, distress, arrest, and failure. Respiratory Compromise is a state in which there is a high likelihood of decompensation into respiratory insufficiency, respiratory failure or death, but in which specific interventions (enhanced monitoring and/or therapies) might prevent or mitigate decompensation.
Respiratory Depression	RD	Respiratory depression is a decrease in the effectiveness of an individual's ventilatory function generally defined as deviation of respiratory rate, pulse oximetry value or arterial carbon dioxide tension from an arbitrary threshold  .
Remote Data Capture	RDC	An interface that allows site users at sites to enter data directly into the study database via a web interface. RDC is an example of Electronic Data Capture method or EDC.
Respiration Rate	RR	The count of breaths per minute based upon the carbon dioxide cycle as measured by capnography.
Serious Adverse Device Effect	SADE	Adverse device effect that has resulted in any of the consequences characteristic of a Serious Adverse Event.
Serious Adverse Event	SAE	An adverse event that a) led to death,

Term	Abbreviation	Definition
		

b) led to serious deterioration in the health of the patient, that either resulted in

c) a life-threatening illness or injury, or

d) a permanent impairment of a body structure or a body function, or

e) in-patient or prolonged hospitalization, or

f) medical or surgical intervention to prevent life-threatening illness or injury or permanent impairment to a body structure or a body function,

g) led to fetal distress, fetal death or a congenital abnormality or birth defect.

Vital Sync™	VS	Vital Sync™ is the brand under which all Integrated Patient Intelligence related products are sold. Included in the brand are the Vital Sync Informatics Manager (VSIM) and the Vital Sync Virtual Patient Monitoring Platform (VPMP).
Vital Sync™ Informatics Manager	VSIM	Is a software solution that resides on a hospitals network that collects, organizes, redistributes, and stores medical device data and device diagnostic information from supported devices to the HIPPA compliant hospital Electronic Medical Record (EMR) and Clinical Information System (CIS).
Vital Sync™ Virtual Patient Monitoring Platform	Vital Sync™ VPMP	A remote continuous patient monitoring software solution allowing EMR, ADT and annunciation connectivity. It allows clinicians to remotely view patient information from multiple device categories (ventilators, capnography monitors, pulse oximeters, depth of consciousness monitors and regional oximetry) on any web-enabled device (smartphones, tablets, desktops, central nurse station).
Vulnerable patient		Individual whose willingness to volunteer in a clinical investigation could be unduly influenced by the expectation, whether justified or not, of benefits associated with participation or of retaliatory response from senior members of a hierarchy in case of refusal to participate.

Term	Abbreviation	Definition
		
EXAMPLE: Individuals with lack of or loss of autonomy due to immaturity or through mental disability, persons in nursing homes, children, impoverished persons, patients in emergency situations, ethnic minority groups, homeless persons, nomads, refugees, and those incapable of giving informed consent. Other vulnerable patients include, for example, members of a group with a hierarchical structure such as university students, subordinate hospital and laboratory personnel, employees of the sponsor, members of the armed forces, and persons kept in detention.
 
This might also include pregnant, parturient or breastfeeding patients and patients hospitalized without their consent.

## 2. Synopsis

Title	LIFEGUARD Study – Continuous Respiratory Monitoring on the General Ward
Clinical Study Type	Prospective, interventional, post-market pilot study
Product Name	

• Capnostream™ 20p and its accessories, including any sensor for SpO2 measurements and filter line for etCO2 sampling.

• Vital Sync™ Virtual Patient Monitoring Platform

• PM1000N-RR Nellcor™ Bedside Respiratory Patient Monitoring System and its accessories, including any sensor for SpO2 measurements.

Sponsor	[REDACTED]
Authorized Representative	[REDACTED]
Investigation Purpose	The purpose of this study is to quantify the incidence and the severity of postoperative RC markers on high risk postsurgical patients on a general ward.
Product Status	Products used are commercially available (CE-Marked) and used within intended use in the participating countries.
Primary Objective(s)	
The primary objective of this study is to quantify the incidence of RC markers in high risk postsurgical patients, using a system comprised of two continuous monitoring devices, connected to a remote monitoring platform.
 
The occurrence of at least one of the following RC markers will be considered as primary endpoint for patients monitored by Capnostream 20p during both study Phases:
 

1. SpO2 ≤ 90% for ≥ 3 minutes.

2. RR ≤ 8 or ≥ 22 bpm for ≥ 3 minutes.

3. etCO2 ≤ 15 or ≥ 60 mmHg for ≥ 3 minutes.

4. Apnea episode lasting > 30 seconds.

	
The occurrence of at least one of the following RC markers will be considered as primary endpoint for patients monitored by PM1000N-RR during both study Phases:
 

1. SpO2 ≤ 90% for ≥ 3 minutes.

2. RR ≤ 8 or ≥ 22 bpm for ≥ 3 minutes.

Secondary Objective(s)	
The study secondary objectives are the following:
 

• To compare the two study Phases in terms of primary endpoint incidence.

• To compare the two study Phases in terms of respiratory AEs and SAE incidence, numbers of ICU transfers and related length of stay, Code blues and RRT responses.

• To evaluate the impact of introducing continuous monitoring devices connected to a remote monitoring platform, on the clinical workflow, defined as the rate of clinical early interventions performed by nurse staff to prevent a potential AE (e.g. patient stimulation, Jaw thrust maneuver, oxygen administration started or increased, medication change, etc.).

• To evaluate the impact of introducing continuous monitoring devices connected to a remote monitoring platform on clinical staff's workflow, defined as clinical staff's satisfaction related to the monitoring system.

• To characterize the predictive values of etCO2, RR, SpO2, plethysmography-derived RR, IPI and EWS in respect to respiratory AEs and other SAE.

 
Related secondary endpoints are:
 

• Incidence of RC markers recorded during each Phase.

• Incidence of respiratory AEs and SAE, number of ICU transfers and related length of stay, Code blues and RRT responses recorded in the two study Phases.

• Average rate of early interventions for patient will be calculated in both study Phases. In Phase I there should only be non- alarm-triggered interventions, as in clinical practice, while in Phase II there should be two sub-groups of clinical early interventions: alarm-triggered and non- alarm-triggered.

• Clinical staff's satisfaction related to each of the monitoring systems introduction in their current workflow will be evaluated through a survey performed at the end of the study.

	

• Sensitivity and specificity of each monitored parameter in predicting and identifying respiratory AEs and SAE will be calculated.

Study Design	
LIFEGUARD is a prospective, two-center, two-phase pilot study. The study population consists of post-surgical patients of adult age on the hospital ward at high risk of developing respiratory and cardiovascular events.
 
During the study Phase I, 70 patients will be 1:1 randomly allocated to Capnostream 20p monitoring system or to PM1000N-RR pulse oximeter monitoring system. In this first phase the alarms of both devices will be silenced and the screen information blinded, to establish a baseline for the incidence of respiratory events in continuously monitored high risk patients. After Phase I and before starting Phase II, each participating site will have a minimum of a 1-month period for familiarization with the unblinded devices, based on a pre-defined hospital protocol for alarm management and escalation policy.
 
During the study Phase II, an additional 140 patients will be 1:1 randomly allocated to Capnostream 20p or to PM1000N-RR monitoring but the screen information will be visible at the bedside and through the Vital Sync™ remote patient monitoring system. The nursing staff will respond to device alarms based on a pre-defined alarm management policy.

Sample Size	Approximately 210 patients will be enrolled in 2 European centers. Each participating center may involve one or more wards in the study, based on its distribution of high-risk patients that may benefit from monitoring.
Inclusion/Exclusion Criteria	
The following criteria must be met for inclusion in the study:
 

1. Non-cardiac post-surgical patients at high risk of developing respiratory and cardiovascular events based on both ARISCAT and POSPOM scores on the hospital ward. In particular, to be enrolled a patient must have: POSPOM score <math>\geq 24</math> (<math>> 3</math> times the mortality average risk) OR ARISCAT score <math>\geq 26</math> (High or intermediate risk for postoperative pulmonary complications).

2. Adult age (<math>\geq 18</math> year old).

3. Patient is able and willing to give informed consent.

 
Exclusion criteria (any of the list below):

	

1. Expected ward length of stay ≤24 hours.

2. Post-surgical patients with American Society of Anesthesiologists physical status (ASA PS) V or higher.

3. Ventilated or intubated patients on the ward.

4. Patient is unwilling or unable to comply fully with study procedures (including non-toleration of the capnography cannula or skin contact allergies to medical grade adhesives) due to any disease condition which can raise doubt about compliance and influencing the study outcome.

5. Patient is a member of a vulnerable population, including legal incapacity or evidence that a patient cannot understand the purpose and risks of the study, regardless of authorized representative support.

6. Patient is participating in another potentially confounding drug or device clinical study.

Study Procedures and Assessments	
Screening will be conducted to identify potential patients who will be admitted to the wards.
 
If the patient is potentially eligible, fully informed and willing to consider participation, written informed consent must be obtained. A review of patient medical files by the investigator is required to determine preliminary eligibility according to patient inclusion and exclusion criteria. Patients are considered a screen failure if inclusion/exclusion criteria are not met prior to commencement of monitoring on the hospital ward.
 
During both study phases, each patient will be monitored for a minimum of 24 hours and up to patient's mobilization or for a maximum of 72 hours.
 
The continuous monitoring data will be recorded for subsequent analysis in conjunction with patient eCRFs. A regular check during the monitoring period should be completed to ensure the etCO2 filter line and SpO2 sensors are appropriately fitted on the patient.
 
A survey will be conducted amongst the participating clinical staff to assess levels of their satisfaction and patient compliance with the different monitoring technologies and the overall feasibility of continuous respiratory monitoring in a general ward setting.

Safety Assessments	Occurrence of any AE with an underlying respiratory cause, SAE or Device Deficiencies will be documented.
Statistics	The sample size calculation is based on the primary endpoint and it was estimated using data from previous studies with a precision-based calculation.

The analysis of primary objective will be based on the proportion of patients with at least one RC marker; it will be reported together with their 95% confidence intervals and separately for each arm and phase of the study. When comparison of clinical primary outcomes is conducted the propensity score methods could be used to control for biases and confounding which may occur due to the nature of this study. For all secondary outcomes the logistic regression model will be used to check potential predictors.

Bivariate odds ratios (ORs) and 95% confidence intervals (95% CIs) will be estimated for each predictor. A multivariate logistic regression model will be performed according to univariate model's results. Other secondary outcomes will be performed using sensitivity and specificity analysis.

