## 4. Objectives and Endpoints

### 4.1. Objectives

#### 4.1.1. Primary Objective and Endpoint

The primary objective of this study is to quantify the incidence of RC markers in high risk postsurgical patients, using a system comprised of two continuous monitoring devices, connected to a remote monitoring platform.

The occurrence of at least one of the following RC markers will be considered as primary endpoint for patients monitored by Capnostream 20p during both study Phases:

1. SpO2 ≤ 90% for ≥ 3 minutes.
2. RR ≤ 8 or ≥ 22 bpm for ≥ 3 minutes.
3. etCO2 ≤ 15 or ≥ 60 mmHg for ≥ 3 minutes.
4. Apnea episode lasting > 30 seconds.

The occurrence of at least one of the following RC markers will be considered as primary endpoint for patients monitored by PM1000N-RR during both study Phases:

1. SpO2 ≤ 90% for ≥ 3 minutes.
2. RR ≤ 8 or ≥ 22 bpm for ≥ 3 minutes.

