### Recommended alarms setting during Study Phase II

To facilitate the detection of RC episodes, the following alarm setting could be programmed at the beginning of the Study Phase II:

Event	Alarm threshold
Low Respiration Rate	$\leq 8$ bpm ( $>30$ sec)
High Respiration Rate	$\geq 22$ bpm ( $>30$ sec)
SpO 2 /Hypoxemia	$\leq 90\%$ ( $>30$ sec)
Low EtCO 2	$\leq 15$ mmHg ( $>30$ sec)
High EtCO 2	$\geq 60$ mmHg ( $>30$ sec)
Apnea	Apnea $> 30$ sec
IPI	IPI $\leq 3 > 30$ sec

Each site will be free to modify the alarms setting according to specific patients' needs or to decrease alarm-related burden.

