### 4. Study Objectives

#### 4.1. Primary Objective

The primary objective of this study is to quantify the incidence of RC markers in high risk postsurgical patients, using a system comprised of two continuous monitoring devices, connected to a remote monitoring platform.

The occurrence of at least one of the following RC markers will be considered as primary endpoint for patients monitored by Capnostream 20p during both study Phases:

- SpO2 ≤ 90% for ≥ 3 minutes (or SpO2 ≤ 90% for < 3 min with an action taken);
- RR ≤ 8 or ≥ 22 bpm for ≥ 3 minutes (or RR ≤ 8 or ≥ 22 bpm for < 3 min with an action taken);
- EtCO2 ≤ 15 or ≥ 60 mmHg for ≥ 3 minutes (or etCO2 ≤ 15 or ≥ 60 mmHg for < 3 min with an action taken);
- Apnea episode lasting > 30 seconds.

The occurrence of at least one of the following RC markers will be considered as primary endpoint for patients monitored by PM1000N during both study Phases:

- SpO2 ≤ 90% for ≥ 3 minutes (or SpO2 ≤ 90% for < 3 min with an action taken);

- RR  $\leq$  8 or  $\geq$  22 bpm for  $\geq$  3 minutes (or RR  $\leq$  8 or  $\geq$  22 bpm for < 3 min with an action taken).

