## 7.9. Evaluation of Objectives

### 7.9.1. Primary Endpoint

The Primary Endpoint of the Study is to quantify the incidence of RC markers in high risk postsurgical patients, using a system comprised of two continuous monitoring devices, connected to a remote monitoring platform. The proportion and rate of “At least one RC marker” event will be calculated and reported.

The “At least one RC marker” event is defined as the occurrence of at least one of the following RC markers:

1.  $\text{SpO}_2 \leq 90\%$  for  $\geq 3$  minutes (or  $\text{SpO}_2 \leq 90\%$  for  $< 3$  min with an action taken);
2.  $\text{RR} \leq 8$  or  $\geq 22$  bpm for  $\geq 3$  minutes (or  $\text{RR} \leq 8$  or  $\geq 22$  bpm for  $< 3$  min with an action taken);
3.  $\text{EtCO}_2 \leq 15$  or  $\geq 60$  mmHg for  $\geq 3$  minutes (or  $\text{EtCO}_2 \leq 15$  or  $\geq 60$  mmHg for  $< 3$  min with an action taken);
4. Apnea episode lasting  $> 30$  seconds.

For patients monitored by PM1000N, only RC markers #1 and #2 will be considered.

RC determination will be assessed by a physician belonging to the “other” site (cross assessment by the sites). This assessment will be made by the analysis of both device and clinical data for each patient. For each patient all potential RC episodes will be derived using the Detection Tool (see Section 10.1) and will be submitted to the other site’s physician in order to adjudicate the potential RC episodes starting from episodes most likely to be RC. The adjudication will stop at the first RC occurring per patient.

The Events’ rates will be computed as (total number of “At least one RC marker” event)/(total number of time-person in PPS) and will be reported separately for each arm and phase of the study. Events’ rates will be displayed together with their 95% confidence interval (95%CI).

If the number of episode per patient result unbalanced, adjusted rates will be reported using the GEE model, together with their 95% confidence interval (95%CI).

If appropriate, also the events’ rates for each RC marker will be reported separately, for each arm and phase of the study.

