### 7.9.2. Secondary Endpoints

The secondary endpoints are:

1. To compare phases in terms of Primary endpoint incidence;
2. To compare phases in terms of respiratory and SAE incidence, number of ICU transfers and related length of stay, Code blues and RRT responses.
3. To evaluate the rate of clinical early interventions performed by nurse staff to prevent a potential AE, introducing continuous monitoring devices connected to a remote monitoring platform;
4. To evaluate the nurses’ satisfaction related to the monitoring system introducing continuous monitoring devices connected to a remote monitoring platform;
5. To establish the Predictive values of  $\text{EtCO}_2$ , RR,  $\text{SpO}_2$ , plethysmography-derived RR, IPI and EWS in respect to respiratory and other SAE.

In order to evaluate secondary **endpoints #1 and #2**, the incidence of events will be reported together with the comparison between phases, by means of the Chi-square test or Fisher exact test for extreme

proportions, as appropriate. If the monitoring/study exposure results different between phases, also the rates of events will be reported, together with the 95% Poisson Confidence Intervals. The Poisson regression model will be used to calculate the Incidence Rate ratio (IRR), with the d-scale option.

For **endpoint #3**, the rate of clinical early interventions will be calculated as (number of early interventions)/(total time-person in FAS) and it will be reported together with the 95% Poisson Confidence Interval.

Early interventions include, as defined in CRF (Monitoring Period):

1. Stimulated subject to breathe;
2. Repositioned/opened airway;
3. Held or reduced Respiratory Depressive (RD);
4. Added or increased supplemental oxygen;
5. Ventilation support;
6. Other

**Endpoint #4** will be evaluated reporting a summary of the nurses' satisfaction answers.

To identify the predictive values for EtCO2, RR, SpO2, plethysmography-derived RR, IPI and EWS, which can predict respiratory and other SAE, a sensitivity analysis will be performed (**endpoint #5**), and the following parameters will be reported, for each RC marker:

1. **Sensitivity** = 
$$\frac{(\# \text{ of clinical events "Yes" and with RC marker "Yes"})}{(\# \text{ of clinical events "Yes"})} = \frac{TP}{(TP+FN)}$$
2. **PPV** = 
$$\frac{(\# \text{ of clinical events "Yes" and with RC marker "Yes"})}{(\# \text{ of events with RC marker "Yes"})} = \frac{TP}{(TP+FP)}$$

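### With the recommended Phase II settings, the apnea alarm and the apnea marker share the > 30 s cut, so the phase comparison on the composite is partly diluted in the Capnostream arm; the SAP's action-taken clause distorts it in both arms.

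*Protocol*

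**What the plan says.** The first secondary objective in the protocol Synopsis is "To compare the two study Phases in terms of primary endpoint incidence". Phase I silences the alarms and blinds the screens; in Phase II staff respond to alarms.

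Protocol 4.1.1 defines the endpoint as at least one marker. For Capnostream patients, SpO2, RR and etCO2 must be out of range for at least 3 minutes, while the fourth marker is "Apnea episode lasting > 30 seconds". PM1000N-RR patients have only the SpO2 and RR markers, which SAP 7.9.1 confirms: "For patients monitored by PM1000N, only RC markers #1 and #2 will be considered".

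Appendix B of the protocol lists recommended Phase II alarms. SpO2, RR, etCO2 and IPI alarm after more than 30 s, and apnea alarms at more than 30 s. The table is advisory: "the following alarm setting could be programmed at the beginning of the Study Phase II", and "Each site will be free to modify the alarms setting".

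The SAP widens the endpoint. In SAP 4.1 and 7.9.1 the SpO2, RR and etCO2 markers each gain an alternative, for example "RR ≤ 8 or ≥ 22 bpm for < 3 min with an action taken". Apnea gains none.

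For endpoints #1 and #2, SAP 7.9.2 says "the incidence of events will be reported together with the comparison between phases", by chi-square or Fisher test. Marker-specific rates by arm and phase are optional in SAP 7.9.1, and no phase test is named for them. Potential episodes are adjudicated by a physician from the other site, and "The adjudication will stop at the first RC occurring per patient".

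**The concern.** The phase comparison asks whether active alarms reduce the proportion of patients with a respiratory compromise marker. It can show a benefit only where a response can act before the event is counted.

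For apnea under the recommended settings there is no such interval. When the apnea alarm sounds, the marker has been met, and under an at-least-one rule nothing done later reverses it. Patients who count through apnea add a block of events to both phases that the apnea alarm cannot move, which pulls the Capnostream contrast toward no effect. PM1000N has no apnea component. Results are reported by arm and phase, and protocol 12.3 plans comparisons between phases within device groups. Alarms could therefore seem to work less well with Capnostream because of how the endpoint is built.

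The SAP definition adds a second distortion. If a short SpO2, RR or etCO2 episode counts because staff acted, a recorded response to an alarm creates the event rather than averting it. Phase II is designed to prompt and record such responses, so this bears more on Phase II than on Phase I, and for SpO2 and RR it does so in both arms.

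**Working it through.** **1. Time from recommended alarm to counted event** (protocol 4.1.1 against Appendix B)

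| Marker | Alarm | Marker met | Interval, protocol definition | Under SAP definition |
|---|---|---|---|---|
| SpO2, RR (both devices) | > 30 s | ≥ 180 s | 180 − 30 = 150 s | none, if an action is recorded |
| etCO2 (Capnostream) | > 30 s | ≥ 180 s | 150 s | none, if an action is recorded |
| Apnea (Capnostream) | > 30 s | > 30 s | 30 − 30 = 0 s | 0 s |

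**2. Illustration under the protocol definition.** The documents give no apnea frequency and no expected phase effect, so every input here is assumed: 3-minute markers in q = 20% of patients in Phase I and 10% in Phase II; apnea in a = 15% (range 5% to 30%), unchanged by phase and independent of the other markers.

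Capnostream composite = 1 − (1 − q)(1 − a).

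- PM1000N: 20% to 10%, a 50% reduction.
- Capnostream, a = 15%: 1 − 0.80 × 0.85 = 32.0% to 1 − 0.90 × 0.85 = 23.5%. Reduction (32.0 − 23.5)/32.0 = 27%.
- Capnostream, a = 5%: 24.0% to 14.5%, 40%.
- Capnostream, a = 30%: 44.0% to 37.0%, 16%.

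Power of the uncorrected two-sided 5% chi-square test, computed exactly on enrolled numbers (the per-protocol set used for endpoint #1 can only be equal or smaller):

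| Contrast | 3-minute markers only | Composite, a = 5% | a = 15% | a = 30% |
|---|---|---|---|---|
| Capnostream, 35 vs 70 | 0.30 | 0.25 | 0.16 | 0.11 |
| Devices pooled, 70 vs 140 | 0.51 | 0.45 | 0.36 | 0.27 |

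In the pooled row the proportions are the mean of the two devices, for example (32.0 + 20)/2 = 26.0% to (23.5 + 10)/2 = 16.75% at a = 15%.

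**3. Let earlier alarms avert some apneas** (base case, apnea 15% in Phase I)

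- A quarter averted (11.25% in Phase II): 1 − 0.90 × 0.8875 = 20.1%, reduction 37%.
- A third averted (10%): 1 − 0.90 × 0.90 = 19.0%, reduction 41%.
- Half averted (7.5%): 1 − 0.90 × 0.925 = 16.75%, reduction 48%, close to the 50% of the other markers.

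**4. The same inputs under the SAP definition** (apnea again 15%, unchanged; no acted-on short episodes in Phase I)

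- Every averted episode had a recorded action: PM1000N 20% to 20% and Capnostream 32% to 32%. Reduction 0% in both.
- Half had a recorded action: Phase II q = 15%. PM1000N 20% to 15%, reduction 25%. Capnostream 32% to 1 − 0.85 × 0.85 = 27.75%, reduction 13%.
- Every averted episode had a recorded action, and a further 10% of patients (independently) have a short episode that staff act on: PM1000N 1 − 0.80 × 0.90 = 28%, a ratio of 28/20 = 1.40. Phase II would look worse.

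**The case against.** **The alarm table is only a suggestion, and other alarms run.** Sites may change the settings. RR, SpO2, etCO2 and IPI alarms and visible screens can prompt action before a first apnea. This stands. A reader might infer that alarm response cannot prevent the apnea marker at all; the documents support that only for the response to the apnea alarm itself at the recommended setting. Step 3 shows that the dilution nearly disappears if half the apneas are averted.

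**The SAP definition overrides the 150 s argument.** This also stands. A reader might infer that the distortion is confined to Capnostream, or that alarms will look better with PM1000N. That follows from the protocol wording only. Under the SAP the SpO2 and RR markers are distorted in both arms, possibly by more than the apnea effect. The zero interval for apnea remains under either definition.

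**The consequence is limited.** The study is a pilot sized for the precision of an incidence estimate, the phase contrast is secondary, and SAP 7.1.1 says arms will not be compared. Marker-specific rates are already allowed. This lowers the weight of the point but does not remove it. The rates are optional, and because adjudication ends at a patient's first event, someone adjudicated on apnea may have no adjudicated status for the other markers.

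**Conclusion.** The concern holds in limited form. Under the recommended settings a response to the apnea alarm cannot stop a Capnostream patient from meeting the composite, so the phase contrast is partly diluted. Under the protocol definition this is specific to the Capnostream arm. Under the SAP definition a recorded response does not avert the SpO2, RR or etCO2 event either, and the contrast is distorted in both arms. The two endpoint definitions conflict and must be reconciled.

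The size cannot be derived from the documents. The 27% against 50%, and the 0% in both arms, rest wholly on the assumed 20%, 10% and 15%, on independence, on apnea being unaffected by phase and, for the 0%, on every averted episode having a recorded action. They show direction and possible scale, not a forecast. The problem described here concerns the phase comparison; the apnea marker can stay in the primary incidence estimate by arm and phase.

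**What to change.** 1. Reconcile the endpoint definition in protocol 4.1.1 with SAP 4.1 and 7.9.1, stating whether short episodes with an action count.
2. Keep the composite for primary incidence and keep its phase comparison.
3. In SAP 7.9.2, endpoint #1, prespecify beside it a phase contrast on SpO2 and RR episodes of at least 3 minutes (plus etCO2 for Capnostream), excluding apnea and the action-taken alternative, by device and phase.
4. State that this contrast uses episodes from the Detection Tool and device memory in both phases, because adjudication stops at the first event per patient.
5. Report apnea by phase as the number of episodes over 30 s per hour of valid capnography. Averted repeat episodes can show in a rate, but not in an at-least-one endpoint.

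No alarm setting needs to change. The data are already collected: protocol 8.10 makes device memory the source for the number and duration of markers. The cost is SAP wording, a few derived variables, one extra contrast and one table. The downside is that the added results rest on unadjudicated device episodes, which may include artefacts such as a displaced sampling line, and should be labelled so.
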